4.2 Potential Benefits

Implantation of the transcatheter heart valve into the IVC may have immediate and long term benefits. In the immediate term, patients may notice stability to the amount of edema they have in their abdomen and legs. In the long term, with protection of the renal veins from the TR, patients may notice improvement in central and peripheral venous congestion, improvement in end organ function including liver and kidneys, and improvement in overall quality of life.

5.0 STUDY PROCEDURES AND SCHEDULE

The study procedures and schedule are listed below. If patients are unable to perform examinations for any reason, justification of this must be provided by the study site PI.

5.1 Pre-Procedure Assessments

The following will be collected in all patients at baseline (within 90 days of procedure, except for Informed Consent which will be obtained prior to beginning screening). Items in bold font are required to determine eligibility and must be performed prior to the Heart Team and Executive Committee meetings.

- **Informed Consent**
- **Medical history.** This will include past medical and surgical history, social history, family history.
- **Physical Exam.** This will include vital signs and weight, head, ears, eyes, nose and throat (HEENT), neck, lungs, cardiovascular, abdomen, genitourinary, gastrointestinal, musculoskeletal, neurological
- **NYHA functional Class** as per The Criteria Committee of the New York Heart Association. *Nomenclature and Criteria for Diagnosis of Diseases of the Heart and Great Vessels*. 9th ed. Boston, Mass: Little, Brown & Co; 1994:253-256
- **Diuretic types and doses**
- Surgical note documenting high risk/inoperable status.

Laboratory Measurements

- CBC with differential (During 6 months of screening and within 21 days of procedure)
- Cardiac Enzymes (Troponin I and/or CK and CKMB) (≤ 72 hours before the procedure)
- **Comprehensive metabolic panel** (within 90 days of procedure)
- Lactate Dehydrogenase (LDH)
- ACT (within 21 days of procedure)
- aPTT (within 21 days of procedure)
- **PT/INR** (within 90 days of procedure)
- Brain Natriuretic Peptide (BNP) (within 21 days of procedure)

Non-Invasive Tests

- ECG (within 21 days of procedure)
- Chest X-ray (portable or PA and lateral) (within 21 days of procedure)
- **Echocardiogram** (Transthoracic) (within 90 days of procedure)
- **Chest and Abdominal CT** (within 90 days of procedure)
- Cardiopulmonary Exercise Stress test ³² (within 90 days of procedure)
- Venous Lower Extremity Duplex Study (within 21 days of procedure)
- **Pulmonary Function Testing** (PFT) (within 90 days of procedure)

Functional Assessments

- 6-minute walk test ³³ (within 90 days of procedure)
- Villalta Scale ^{25,26} (within 21 days of procedure)
- EORTC QLQ-C30 ²⁷ (within 21 days of procedure)
- ESAS-AM ²⁸ (within 21 days of procedure)
- Kansas City Cardiomyopathy Questionnaire (KCCQ) ²² (within 21 days of procedure)

Invasive Tests

- **Left Heart Catheterization with or without LV gram and IVUS.** (Within one year of baseline)
- **Right Heart Catheterization** (within 90 days of procedure)

5.2 PROCEDURE Description

Procedure Assessments

The following tests and assessments will be performed on the day of or during the procedure:

Total procedure time is defined as the time from skin incision to the time of skin incision access closure.

The following invasive hemodynamic data must be collected pre and post implant:

- Echo assessments of severity of tricuspid regurgitation and RV function
- Fluoroscopic imaging of the implanted valve
- Medications given for cardiovascular effect including anti-platelet/anti-thrombins
- Event assessment

5.2.1 Placement of percutaneous aortic valve in the inferior vena cava

The procedure will be performed in the cath lab/ hybrid Cath Lab/OR under general anesthesia and transesophageal echocardiographic as well as fluoroscopic guidance.

Measurements obtained prior to the procedure

The diameter of the IVC at the RA/IVC junction will be measured prior to the procedure by contrast CT or rotational cine fluoroscopy to determine sizing of the stent which will be placed in the IVC. In order to avoid compromise of the hepatic veins with the valve skirt, distances from the RA/IVC junction to the hepatic veins will be measured by contrast CT.

Procedure

The procedure will be performed through the right or left femoral vein using standard technique. We will use fluoroscopic and ultrasonographic landmarks to locate the right femoral vein and using a micropuncture needle for initial access, and then will place an 8F sheath in the right Common Femoral vein. We will then perform a cavogram using a Omnipulse catheter. The Edwards expandable sheath and delivery system will be placed into the right femoral vein. A 5-French sheath will be placed in the right or left radial femoral artery to monitor arterial pressure and secure arterial access throughout the procedure, and a catheter may or may not be placed in the right internal jugular vein. Heparin will be administered to achieve an activated clotting time (ACT) between 250-300s. To achieve stable position of the valve in the IVC, we will perform pre-stenting of the IVC with either a balloon expandable or self-expandable stent according to standard technique. A repeat cavogram with an Omnipulse catheter will be done to delineate the takeoff of the hepatic veins prior to valve implantation. When positioning is confirmed the Edwards or balloon in balloon (BIB) delivery system will be deployed into the suprahepatic segment of the IVC by standard technique. Right ventricular (RV) angiography from IJ access and echocardiogram will be performed to confirm intact valve function and any evidence of regurgitation. At the end of the procedure, the venous sheath will be removed and periclose devices will be deployed or a figure of 8 suture will be used to achieve adequate hemostasis. The arterial sheath will be removed with closure devices or with direct manual pressure.

Anticoagulation Regimen:

Pre-procedure: Patients in atrial fibrillation on warfarin may be bridged with LMW or UF heparin prior to the procedure. During the procedure: IV heparin will be given to maintain ACT > 250 sec. Patients may be bridged to a therapeutic INR with either heparin or Lovenox post-procedurally.

Recommended Antiplatelet/Anticoagulation Regimen

Aspirin 81 mg p.o. daily indefinitely plus warfarin therapy to maintain an INR between 2-3. In those patients with severe hepatic dysfunction whom have elevated INR at baseline, ASA 81mg will be continued and the level of additional anti-coagulation will be decided on a case by case basis.

Radiation precautions:

Radiation exposure will be documented at each study visit in the CRF, with options to record whether chest x-ray, including additional plain x-rays, CT scans and all fluoroscopy procedures were performed. In the event that a dose isn't recorded; such as a plain X-ray, an average dose will be assigned for each applicable test. A trigger will be applied in the database such that when the cumulative estimated radiation exposure calculation exceeds 150 to 250 Gy/cm².

Additional precautions: for any study patient, the site coordinator and investigator will be notified and a follow-up visit advised to assess patient for skin reaction. Substantial radiation dose level (SRDL) - The operator should be notified promptly if SRDL was exceeded. The SRDL is a trigger level to initiate follow-up of a radiation dose that might produce a clinically relevant injury in an average patient. Some suggested values for the SRDL are a skin dose of 3 Gy, a KAP of 500 Gy/cm², or an air kerma at the interventional reference point of 5 Gy (NCRP 2010). For cardiology procedures, a level greater than 2 Gy will be noted and close follow up will be performed to evaluate for skin toxicity.

The operator should write an appropriate note in the patient's medical record, stating that a substantial radiation dose has been administered, and indicating the reason. This information may be included in the post procedure notes. Patients with reported KAP between 150 and 250 Gy/cm² must be further evaluated for radiation injury and the event must be reported as a serious adverse event in the case report form.

Acute evaluation - When the SRDL has been exceeded, clinical follow-up essential for early detection and management of skin injuries. The patient should be advised of the possibility of a skin injury due to a tissue reaction, and should be told to examine the beam entrance site at 2-4 weeks after the procedure. The operator should be notified if any skin changes are seen. Patients who have not previously notified the operator should be contacted by telephone at approximately 30 days after the procedure, in order to ensure that a skin injury is not missed.

Long-term evaluation - If a skin injury is suspected, the interventionalist should see the patient at an office visit, and should arrange for appropriate follow-up care. The physician responsible for the patient's care should be informed of the possibility of radiation effects.

5.3 Post-Procedure assessments:

Study patients will be continuously monitored clinically, hemodynamically, and electrocardiographically during catheterization for all local, systemic side effects and complications. After completion of the procedure, patients will be admitted to the hospital for further monitoring.

- Physical Exam. This will include vital signs and weight, head, ears, eyes, nose and throat (HEENT), neck, lungs, cardiovascular, abdomen, genitourinary, gastrointestinal, musculoskeletal, neurological
- NYHA functional Class as per The Criteria Committee of the New York Heart Association. *Nomenclature and Criteria for Diagnosis of Diseases of the Heart and Great Vessels*. 9th ed. Boston, Mass: Little, Brown & Co; 1994:253-256
- Diuretic types and doses
- Event assessment as per VARC-2¹⁹.

Laboratory Measurements

- CBC with differential
- Cardiac Enzymes (Troponin I and/or CK and CKMB) every 8 hours x3
- Comprehensive metabolic panel
- Lactate Dehydrogenase (LDH)
- ACT (optional)
- PT/INR
- Brain Natriuretic Peptide (BNP)

Non-Invasive Tests

- ECG
- Echocardiogram (Transthoracic)

5.4 Discharge Procedures

The following data will be collected for all study patients as close to the date of discharge as possible. A post-procedure echocardiogram will also be performed prior to discharge. If a patient is discharged over a weekend or holiday, the discharge tests may be completed on the last weekday prior to discharge.

Systems:

- Physical Exam. This will include vital signs and weight, head, ears, eyes, nose and throat (HEENT), neck, lungs, cardiovascular, abdomen, genitourinary, gastrointestinal, musculoskeletal, neurological
- NYHA functional Class as per The Criteria Committee of the New York Heart Association. *Nomenclature and Criteria for Diagnosis of Diseases of the Heart and Great Vessels*. 9th ed. Boston, Mass: Little, Brown & Co; 1994:253-256
- Diuretic types and doses
- Event assessment as per VARC-2 ¹⁹.

Laboratory Measurements

- CBC with differential
- Comprehensive metabolic panel
- Brain Natriuretic Peptide (BNP)
- Haptoglobin
- Lactate dehydrogenase (LDH)

5.5 Follow-Up Procedures

Patients will follow up at 1, 6 and 12 months with a member of the study team. The following information will be collected at follow up visits.

Systems:

- Physical Exam. This will include vital signs and weight, head, ears, eyes, nose and throat (HEENT), neck, lungs, cardiovascular, abdomen, genitourinary, gastrointestinal, musculoskeletal, neurological
- NYHA functional Class as per The Criteria Committee of the New York Heart Association. *Nomenclature and Criteria for Diagnosis of Diseases of the Heart and Great Vessels*. 9th ed. Boston, Mass: Little, Brown & Co; 1994:253-256
- Diuretic types and doses
- Event assessment as per VARC-2 ¹⁹.

Laboratory Measurements

- CBC with differential
- Comprehensive metabolic panel
- Brain Natriuretic Peptide (BNP)
- Haptoglobin
- Lactate Dehydrogenase (LDH)

Non-Invasive Tests

- ECG
- Chest X-ray (portable or PA and lateral)
- Echocardiogram (Transthoracic)
- Chest and Abdominal CT (6-months only)
- Cardiopulmonary Exercise Stress test ³² (6-months only)

Functional Assessments

- 6-minute walk test ³³
- Villalta Scale ^{25,26}
- EORTC QLQ-C30 ²⁷
- ESAS-AM ²⁸
- Kansas City Cardiomyopathy Questionnaire (KCCQ) ²²

Invasive studies

- Right heart catheterization (6-months only)

5.6 Annual Study Visit, Final Study Visit, premature discontinuation or unscheduled study visit

The following variables will be collected for the above parameters.

- Physical Exam. This will include vital signs and weight, head, ears, eyes, nose and throat (HEENT), neck, lungs, cardiovascular, abdomen, genitourinary, gastrointestinal, musculoskeletal, neurological
- NYHA functional Class as per The Criteria Committee of the New York Heart Association. *Nomenclature and Criteria for Diagnosis of Diseases of the Heart and Great Vessels*. 9th ed. Boston, Mass: Little, Brown & Co; 1994:253-256
- Diuretic types and doses
- Event assessment as per VARC-2 ¹⁹.

Table 1: Summary Schedule of Procedure and Follow-Up

	Baseline	During the procedure	24 hrs. after the procedure	7 days after procedure or at discharge	At 30 days (+/- 7 days)	At 6 months (+/- 14 days)	At 1 yr (+/- 21 days)	Annually up to 5 years (+/- 21 day)	Premature discontinuation or unscheduled visit
Informed Consent	Xb†								
Medical History	Xb†								
Physical Exam (incl. Vital signs)	Xb†		X	X	X	X	X	X	X
NYHA Class	Xb†		X	X	X	X	X	X	X
Diuretic types and doses	Xb†		X	X	X	X	X	X	X
Event Assessment	Xb		X	X	X	X	X	X	X
Surgical note documenting high risk/inoperable status	Xb†								

Laboratory Measurements								
CBC with Differential	Xd		x	X		X	X	
Cardiac Enzymes (Troponin I and/or CK and CK-MB)	Xe		X (every 8 hours x 3)					
Comprehensive Metabolic Panel	Xb†		X	X	X	X	X	
LDH (to assess hemolysis)	Xc		X	X	X	X	X	
ACT^		X*	X*					
aPTT	Xc	X*						
PT/ INR	Xb†		X					
Brain Natriuretic Peptide (BNP)	Xc		x	X	X	X	X	
Haptoglobin	Xc			X	X	X	X	
Non-Invasive Tests								
ECG	Xc		X		X	X	X	
Chest X-ray	Xc				X	X	X	
Echocardiogram - TTE or TEE	Xb†	X	X		X	X	X	
Chest and/or Abdominal CT	Xa†					X		
Cardiopulmonary Exercise Stress test	Xb					X		
Venous Lower Extremity Duplex Study	Xc							
Pulmonary Function Test (PFT)	Xb†							
Functional Assessments								
6-Minute Walk Test	Xb				X	X	X	
Quality of Life (Kansas City Cardiomyopathy Questionnaire (KCCQ))	Xc				X	X	X	
Villalta Scale	Xc				X	X	X	
EORTC QLQ-C30	Xc				X	X	X	
ESAS-AM	Xc				X	X	X	
Invasive Tests								
Left Heart Catheterization w/wo LV gram and IVUS ^a	Xa†	X*						
Right Heart Catheterization	Xb†	X				X		

- a. The following assessment will be collected within one year of procedure day.
- b. The following assessments will be completed within 90 days before the procedure day
- c. The following assessments will be completed within 21 days before the procedure.
- d. The following assessment needs to be done during the 6 months screening and within 21 days before the procedure.
- e. CK/CKMB and/or Troponins ≤ 72 hours before the procedure
- f. Right heart catheterization only

* Optional

† Required prior to Heart Team and Executive Committee meetings to determine eligibility

5.7 Patient Withdrawal

All study patients are required to complete clinical follow-up for all designated study visits. A careful review of these requirements must be communicated to the patient and family members prior to obtaining the study consent. Patients who cannot make study visits due to physical or geographical constraints should be encouraged to complete as many assessments within the planned visit as possible. A study patient that has been withdrawn from the study will not be replaced and may impact the ITT analysis.

Every patient should be encouraged to remain in the study until they have completed the protocol required follow-up period. If the patient discontinues prematurely from the study, the reason for discontinuation must be documented. Possible reasons for premature discontinuation may include, but are not limited to the following:

- Withdrawal of consent: Patient decides to withdraw from the study.
- Lost to follow-up: All patients should be encouraged to return to the clinic for evaluation during long term follow-up. The patient will be considered lost to follow-up if this communication is unsuccessful. Patients who discontinue prematurely will be included in the analysis of results, and will not be replaced.
- Death registries: In the event of a patient withdrawal or lost to follow-up, the sponsor may opt to obtain the death certificate, search the Social Security Death Index and/or other death registries to obtain survival information.

6.0 ADMINISTRATIVE RESPONSIBILITIES

6.1 Institutional Review Board (IRB) Information

This protocol and the informed consent must be reviewed and approved by the appropriate IRB before enrollment of patients. All changes to the protocol must be approved in writing by the IRB before the change is implemented.

6.1.1 Institutional Review Board Approval Letter

Institutional Review Board (IRB) approval to participate in this trial is required from each institution participating in this investigation. Prior to patient enrollment, a signed copy of the IRB approval letter must be submitted to the sponsor investigator certifying trial approval. Investigators are responsible for submitting and obtaining initial and continuing review of the trial at least annually unless otherwise directed by their IRB.

6.2 Informed Consent

Informed consent is mandatory and must be obtained from all study patients prior to their participation in this trial. Any modifications to the Informed Consent Form must be approved by the IRB. A copy of the IRB approved Informed Consent Form along with a copy of each patient's signed consent form must be maintained by each investigator in a designated clinical trial administrative file. A signed copy of the consent form must be given to each patient.

6.3 Confidentiality

All information and data collected in this trial will be considered confidential. Only authorized data management center personnel will have access to these confidential files. Authorized personnel from the regulatory authorities have the right to inspect and copy all records pertinent to this trial. All data used in the analysis and reporting of this evaluation will be without identifiable reference to the patient.

7.0 ADVERSE EVENT REPORTING

7.1 Adverse events:

An adverse event (AE) is any untoward medical event in a patient and does not necessarily have a causal relationship with the use of the device. Symptoms or medically significant laboratory or instrumental abnormalities of a preexisting disease, such as hypertension or other disease, should not be considered adverse events but must be documented in the medical history if clinically significant. New symptoms or laboratory abnormalities, however, as well as worsening of existing ones, are considered adverse events. Study device causality for adverse events will be graded as unlikely, possible or probably.

7.2 Serious Adverse Events

A serious adverse event (SAE) is any untoward medical occurrence that:

- results in death
- is life-threatening, i.e., an event that, in the view of the investigator, places the subject at immediate risk of death from the event as it occurred (it does not include an event that could have caused death if it had been more severe)
- requires inpatient hospitalization or prolongs the existing hospitalization
- results in persistent or significant disability or incapacity, where disability is defined as a substantial disruption of a person's ability to conduct normal life functions, either reported or defined as per clinical judgment
- is a congenital anomaly or birth defect (if exposure to product just before conception or during pregnancy resulted in an adverse outcome in the child)

All investigators will be responsible for reporting serious adverse events to the sponsor and their reviewing IRBs in accordance with local guidelines. In addition, all SAEs will be reviewed by an independent Data Safety Monitoring Board (DSMB) in accordance with their charter. (An SAE will be reported to the Sponsor and DSMB Chair within 24 hours from when the event was discovered and the SAE CRF will be submitted no later than ten (10) days after the SAE was discovered) Study device causality for SAE's will be graded as unlikely, possible or probably.

7.3 Non-Serious Adverse Events

A non-serious adverse event is any AE that does not meet the criteria listed above for a serious adverse event, or the outcome (subject treatment, life-threatening condition, hospitalization, recovery) cannot be determined with the information provided. Non-serious AEs will be documented on the AE log and will be reported to IRB per local regulations.

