7.6 Unanticipated Adverse Device Effects

Unanticipated adverse device effects (UADE) are defined as any serious adverse effect on health or safety or any life-threatening problem or death caused by, or associated with, a device, if that effect, problem, or death was not previously identified in nature, severity, or degree of incidence in the investigational plan or application (including a supplementary plan or application), or any other unanticipated serious problem associated with a device that relates to the rights, safety, or welfare of study patients.

All UADEs must be reported to the FDA immediately upon the Investigator's awareness of the event. The AE Forms of the CRF must be completed within 7 working days for all UADEs. The Investigator is also responsible for notifying his/her IRB of all UADEs occurring at his/her site no later than 10 days after the investigator first learns of the effect (and any additional information as required by EC/IRB or local regulations). All UADE adverse events must be followed until resolution or until a stable clinical endpoint is reached. All required treatments and outcomes of the UADE adverse event must be recorded.

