		____/____ ____:____ — ____:____	 1 Ongoing  2 Resolved  3 Pt. Died	____/____ ____:____ — ____:____	 1 Mild  2 Moderate  3 Severe  4 SAE*	 0 NO  1 YES**	 0 NO  1 Stopped temporarily  2 Stopped Permanently	 1 Unlikely  2 Possibly  3 Probably	
		____/____ ____:____ — ____:____	 1 Ongoing  2 Resolved  3 Pt. Died	____/____ ____:____ — ____:____	 1 Mild  2 Moderate  3 Severe  4 SAE*	 0 NO  1 YES**	 0 NO  1 Stopped temporarily  2 Stopped Permanently	 1 Unlikely  2 Possibly  3 Probably	
		____/____ ____:____ — ____:____	 1 Ongoing  2 Resolved  3 Pt. Died	____/____ ____:____ — ____:____	 1 Mild  2 Moderate  3 Severe  4 SAE*	 0 NO  1 YES**	 0 NO  1 Stopped temporarily  2 Stopped Permanently	 1 Unlikely  2 Possibly  3 Probably	

Describe:
 <hr/> 
If event is SAE then submit AE form to medical reviewer within 24 hours. **If YES and device related, complete UADE form
									

UNANTICIPATED ADVERSE DEVICE EFFECT FORM

1. Date form completed		— / — / — —	MO	DAY	4-Digit YEAR			
2. Date and time of onset:		— / — / — —	MO	DAY	4-Digit YEAR	— : —	(Military time)	
3. Has event resolved?  YES  NO		If YES, Date/Time resolved: — / — / — —						
		MO	DAY	4-Digit YEAR	— : —	(Military time)		
4. Relationship to study device: (choose one)		 NOT related	 Probably related	 Unknown				

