		 Possibly related	 Definitely related					
If related, (1, 2 or 3) then specify Serial ID# for device _____								
5. In your opinion, is this a UADE*  YES  NO								
6. Action taken (Check all that apply)		 YES  NO None						
		 YES  NO Medication, specify: _____						
		 YES  NO Surgery, specify _____						
		 YES  NO Other, specify _____						
7. Severity (Check one)		 Mild  Moderate  Severe  Life threatening						
8. Outcome (Check all that apply)								
YES	NO			YES	NO			
		A. Continuing WITHOUT treatment				E. Recovered WITHOUT treatment		
		B. Continuing WITH treatment				F. Recovered WITH treatment		
		C. Continuing with sequelae, specify: _____				G. Patient expired (attach copy of autopsy or death summary)		
		D. Temporary disability				H. Permanent disability		
9. Description of adverse effect: _____								
* An Unanticipated Adverse Device Effect (UADE) is any serious adverse effect on health or safety, or any life-threatening problem or death caused by or associated with this device, if that effect, problem, or death is not identified in nature, severity, or degree of incidence in this Investigational Study; or any other unanticipated serious problem associated with this device that relates to the rights, safety or welfare of the subjects. UADEs must be reported to the principal investigator and the IRB within 10 working days.								
I verify that the form completed for this UADE is accurate and representative of the data available in source documentation.								
Investigator's signature				Date — / — / — — MO DAY 4-Digit YEAR				

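### Section 7.3 classes an adverse event of undetermined seriousness as non-serious, so it loses the 24-hour notice to the sponsor and DSMB Chair that Section 7.2 requires

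*Combined protocol and SAP*

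**What the plan says.** Section 7.2 lists the criteria that make an event serious. They include death, threat to life in the investigator's view, and an event that "requires inpatient hospitalization or prolongs the existing hospitalization". It then sets the clock and the recipients: "An SAE will be reported to the Sponsor and DSMB Chair within 24 hours from when the event was discovered". The same section commits the DSMB to reviewing every SAE under its charter.

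Section 7.3 defines the complement in two limbs. The first is the usual one: "A non-serious adverse event is any AE that does not meet the criteria listed above for a serious adverse event". The second is joined to it by a disjunction: "or the outcome (subject treatment, life-threatening condition, hospitalization, recovery) cannot be determined with the information provided". The consequence of landing in either limb is: "Non-serious AEs will be documented on the AE log and will be reported to IRB per local regulations".

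The two forms that follow the reference list carry their own instructions. The footnote of the Adverse Event form reads: "If event is SAE then submit AE form to medical reviewer within 24 hours". The Unanticipated Adverse Device Effect (UADE) form states: "UADEs must be reported to the principal investigator and the IRB within 10 working days". Section 7.6 requires the investigator to notify the IRB of a UADE "no later than 10 days after the investigator first learns of the effect" and asks for immediate reporting to the FDA.

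**The concern.** A seriousness definition needs a default for the case where the facts are not yet in. Here the default runs in the less cautious direction. Suppose a relative reports that a patient was taken to an outside hospital, and no records can be had. Whether the patient was admitted, or was in danger, is exactly what is unknown. Read as written, Section 7.3 makes this a non-serious event.

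Events managed away from the study site are the ones most likely to arrive with gaps. In an off-label implant study of at most 15 patients, one or two such events are a material part of the safety record. Section 2.3 says accrual will be suspended at once if adverse events other than death look excessive, and Section 4.1.3 pauses the trial if valve thrombosis reaches 30% of patients at 6 months. Both work only as fast as non-fatal events are recognised and passed on.

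**Working it through.** No figure in the plan needs reproducing. The check is a comparison of text, plus one comparison of deadlines.

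1. **Overlap of the two definitions.** The unknowns listed in 7.3 are treatment, life threat, hospitalization and recovery. Life threat and hospitalization are also SAE criteria in 7.2. When the unknown is whether one of those two criteria was met, 7.3 settles the question as non-serious.

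2. **Direct contradiction.** The limbs of 7.3 are alternatives, so an unknown outcome is enough by itself. An event with a confirmed admission but unknown recovery is serious under 7.2 and non-serious under the second limb of 7.3. Nothing says which section prevails.

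3. **What changes with the label.**
   - Serious (7.2): sponsor and DSMB Chair within 24 hours of discovery; SAE case report form within 10 days; DSMB review of each case.
   - Undetermined (7.3): AE log and IRB under local rules; no sponsor or DSMB recipient and no deadline.

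4. **Route back.** Section 7 has no provisional-serious rule, no time limit for a query and no upgrade step. The AE form offers SAE as one option in its intensity field but none for undetermined seriousness. The 24-hour clock in 7.2 runs from discovery of the event, so an event logged as non-serious and later found serious may already be past it.

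5. **What still reaches the DSMB.** Section 4.1.2 has it review all safety data, and Section 8.3 gives it access to those data. Section 7.4 sends unanticipated events to the sponsor, IRBs and FDA within 10 days. Section 9.4 has the sponsor pass unanticipated events on to the DSMB, with no stated clock. None of these gives the DSMB Chair notice within 24 hours. An anticipated event of unclear seriousness falls outside 7.4.

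6. **Which safety rules are affected.** The boundaries in 4.1.3 count deaths. Death is an SAE under 7.2 and is not among the unknowns in 7.3. The thrombosis pause does not depend on seriousness, so a logged event still counts once it is read; what can change is when. Illustrating with the plan's own numbers of patients, 30% of 6 is 1.8, so 2 events, and 30% of 15 is 4.5, so 5 events. One late event is therefore half or a fifth of the count needed.

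7. **Forms.** The AE form keeps the 24 hours but names only a medical reviewer, a role not defined in the available text. For UADEs the IRB deadlines differ. Ten working days, ignoring holidays, is 14 calendar days from a weekday start, 13 from a Saturday and 12 from a Sunday. Against 10 days in 7.6 the form allows 2 to 4 days more. Section 7.6 uses working days for a different deadline, so its unqualified days read as calendar days. The UADE definition in 7.6 is framed around serious effects, so the 24-hour sponsor notice in 7.2 applies as well; the form does not mention it.

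**The case against.** The best defence is that little is really hidden. Data go into a central electronic system (8.1, 10.1), and the coordinating center oversees their collection and verification (10.6). Section 4.1.2 expects frequent DSMB review and lets the board meet at any time. Section 2.3 has the trial PI and coordinator monitor adverse events throughout, working with the DSMB. Section 7.4 judges unanticipated events against the product information and on-label use, and this is an off-label site, so many device events might qualify for its 10-day route. Once records show an admission, 7.2 applies. All of this stands, and it limits the harm to loss of expedited notice and of assured case review. It does not restore the 24-hour notice.

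A reader might go further in four ways that the documents do not support.

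- **That the mortality stopping rule is weakened.** Deaths are reportable under 7.2 whatever 7.3 says.
- **That notice could be delayed until the next six-monthly review, with a countable number of implants in between.** The six-monthly review in 4.1.3 is a minimum and sits beside the looks at set patient numbers and the routes above. The documents give no accrual rate from which to count implants.
- **That the AE form takes the DSMB Chair out of the chain.** The form omits the Chair and the sponsor, but nothing in it cancels 7.2. The medical reviewer may be defined in text not available here.
- **That Appendix B sets an opposite default by counting death of unknown cause as cardiovascular.** That rule classifies cause of death. It is not a reporting rule and does not conflict with 7.3.

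**Conclusion.** The concern holds on the plain wording. Section 7.3 states a rule, not merely a gap: an event whose life-threatening or hospitalization status is unknown is non-serious. Following it removes the 24-hour notice to the sponsor and DSMB Chair and the guaranteed DSMB look at the case. Where seriousness is clear but another outcome is not, 7.2 and 7.3 contradict each other.

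The size is a change from a 24-hour deadline to no stated sponsor or DSMB deadline, or to 10 days to the sponsor if the event is judged unanticipated. The number of events affected cannot be estimated from the documents. The rule bears on recognising non-fatal harm promptly. No endpoint in Section 2.4 is defined by seriousness, so the planned endpoint estimates are not at issue.

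The form mismatches are real but secondary: an incomplete recipient list on the AE form, and an IRB deadline on the UADE form that is 2 to 4 days longer than in 7.6. The conclusion assumes that no charter, monitoring plan or removed text already supplies a provisional-serious rule.

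**What to change.** - **Section 7.3:** delete the second limb, so that non-serious means only that the 7.2 criteria are not met.
- **Section 7.2:** state that an event whose seriousness cannot yet be determined is reported there as a provisional SAE, on the same 24-hour clock to the sponsor and DSMB Chair, and reclassified with a documented reason when information arrives.
- **AE form footnote:** name the sponsor and DSMB Chair as recipients, to match 7.2. If the medical reviewer is kept, say who that is and that this notice is additional.
- **UADE form:** reconcile the IRB deadline with 7.6 so that one figure appears in both places, and restate the 24-hour sponsor notice from 7.2.

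The cost is a short wording amendment and two revised forms. Sites will send a few provisional SAE reports that are later downgraded; with at most 15 patients that burden should be small.
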